CinnaPoietin[®] Clinical Trial Protocol

A Phase III, randomized, two armed, multicenter, parallel, double blind (patient and assessor blinded), active controlled non inferiority clinical trial to determine the non-inferior therapeutic efficacy and safety between CinnaPoietin[®] (Beta erythropoietin) and Eprex[®] (epoetin alpha) on treatment of anemia in ESRD hemodialysis patients.

Date: 23 August 2015

NCT number: NCT03408639

Cinnapoietin[®] clinical trial synopsis

Title	A Phase III, randomized, two armed, multicenter, parallel, double blind (patient and assessor blinded), active controlled non inferiority clinical trial to determine the non-inferior therapeutic efficacy and safety between CinnaPoietin [®] (Beta erythropoietin) and Eprex [®] (epoetin alpha) on the treatment of anemia in ESRD hemodialysis patients
Aim of Study (Primary objective)	Determination of non-inferior efficacy of Beta erythropoietin (CinnaPoietin [®]) compared with Eprex [®] (epoetin alpha) in correction of hemoglobin levels of anemic patients with chronic kidney disease (CKD) under hemodialysis
Secondary objectives	The secondary outcomes of interest include assessment of efficacy and safety of Beta erythropoietin (CinnaPoietin [®]).
Study Design	The study is designed as phase III, randomized, two armed, multicenter, parallel, double blind (patient and assessor blinded), active controlled non inferiority clinical trial with primary outcome of hemoglobin level change in anemic patients with CKD under hemodialysis.
Registration	This study is planned to be registered in Iranian Registry of Clinical Trial (IRCT)
Sponsor	CinnaGen Co
Contract Research Organization (CRO)	CRO Trial, Tehran University of Medical Sciences, Tehran, Iran.
Principal Investigator	Investigator name: [name] [name] Affiliation: Nephrology Research Center, Tehran University of Medical Sciences, Tehran, Iran Recruitment centers: Ghiasi Hospital


Co-investigators and recruitment centers
	
1. [name] Affiliation: Department of Nephrology, Kerman University of Medical Sciences, Kerman, Iran. Recruitment centers: 1. SHAFa Hospital 2. Javad Ol Aemeh Hospital
 
2. [name] Affiliation: Nephrology and Urology Research Center, Baqiyatallah University of Medical Sciences, Tehran, Iran Recruitment centers: 1. Milad Hospital
 
3. [name] Affiliation: Hasheminejad Kidney Center, Iran University of Medical Sciences, Tehran, Iran Recruitment centers: 1.Hashemi Nezhad Hospital
 
4. [name] Affiliation: Hasheminejad Kidney Center, Iran University of Medical Sciences, Tehran, Iran Recruitment centers: 1. Hashemi Nezhad Hospital
 
5. [name] Affiliation: Imam Hossein Hospital, Shahid Beheshti University of Medical Sciences, Tehran, Iran Recruitment centers: 1. Imam Hossein Hospital 2. Madar Hospital
 
6. [name] [name] Affiliation: Nephro-Urology Research Center, Shiraz University of Medical Sciences, Shiraz, Iran Recruitment centers: 1. Haj Ebrahimi dialysis center

Investigational Drug
	
Erythropietin beta biosimilar (CinnaGen co, Iran)

Comparator
	
Eprex[®] (erythropoietin alfa) (the reference drug, produced by Janssen-Cilag)

Sample size
	
156 patients will be equally (1:1) divided into intervention arms (78 in each considering drop out) for achieving 80% power in order to determine non-inferiority using a one-sided, independent sample t-test. The margin of non-inferiority is -1.

	
The true difference between the means is assumed to be -0.5. The significance level (alpha) of the test is 0.05. The data are drawn from populations with standard deviations of 1.2 and 1.2.


Eligibility criteria
	
Inclusion Criteria:
 
 • Aged between 18 and 70 • ESRD patients who are on hemodialysis for ≥ 3 months. • Hb level 8- 11.5 g/dl • Patients are on adequate hemodialysis: the minimally adequate dose of hemodialysis given 3 times per week should be a spKt/V (single-pool delivered Kt/V; clearance of urea x dialysis time/volume of distribution) of 1.2 per dialysis. For treatment periods of less than 5 hours, an alternative minimum dose is a urea reduction rate (URR) of 65%. All types of hemodialysis systems and hemodiafiltration, including high-flux membranes are allowed as long as there is no plan to change the patient's regimen during the study. • Sufficient iron stores, defined as serum ferritin ≥ 200 ng/ml and transferrin saturation $\geq 20\%$. (Patients not meeting these criteria may receive iron supplementation therapy during the Screening and stabilization period to appropriately correct their iron store deficiency to meet the criterion required for randomization); • Ability to comply with study medication use, study visits, and study procedures as judged by the investigator; • Females of childbearing potential agree to use an acceptable method of birth control (e.g., abstinence, hormonal or barrier methods, partner sterilization, or IUD) for the duration of the study. • Qualified and willing to sign the informed consent form with the commitment of complying with all the scheduled visits, and study procedures as judged by the investigator; • In any circumstances that potential participants are not able to give consent, it may be given by responsible parents or guardian. 
Exclusion criteria
 
 • Uncontrolled hypertension (defined as pre-dialysis diastolic blood pressure ≥ 100 mmHg or systolic blood pressure ≥ 180 mmHg); • Anemia secondary to other causes different to the CKD (e.g. multiple myeloma, aplastic anemia, leukemia....)

- Decompensated liver failure;
- Clinical evidence of concurrent uncontrolled hyperparathyroidism (defined as serum parathyroid hormone (iPTH) > 800 pg/ml);
- Heart failure [New York Heart Association (NYHA) class III and IV];
- Unstable angina pectoris, active cardiac disease, stroke and/or cardiac infarction within the last six months;
- History of or active blood coagulation disorders including DVT, PTE, native access Thrombosis during last six months.
- Thrombocytosis (platelet count > 500,000/ μ l);
- Thrombocytopenia (platelet count < 100,000/ μ l);
- White blood cell count < 3,000/ μ l);
- White blood cell count >15,000/ μ l)
- Recent Bleeding (acute or chronic bleeding within three months prior to screening);
- Suspicion of or confirmed occult bleeding (increased reticulocyte count);
- Clinical evidence of concurrent systemic infection, or inflammatory disease (e.g; diabetic foot, bed sore, access infection, CRP> 30 mg/l)
- Currently receiving treatment for epilepsy;
- Major surgery within 3 months prior to randomization and during the conduct of the trial (except vascular access surgery);
- Concomitant immunosuppressive therapy; patients on a short course of steroids (up to 7 days), topical or intranasal steroids are allowed in the study;
- History of any malignant disease within the last 5 years (except excised non-melanoma skin cancer);
- Women who are pregnant or breastfeeding;
- Known history of severe drug-related allergies;
- Known history of drug related allergy to Erythropoietin or one of the ingredients of the test or the reference products or hypersensitivity to mammalian-derived products;
- Transplant received within one year prior to the start of the study;

	
 • Simultaneous participation in another clinical study or having received an Investigational Medicinal Product within three months before randomization in this study. • Psychiatric, addictive (drugs or alcohol) or any other disorder that compromises the ability to give an informed consent; • Any red blood cell transfusion during the last 3 months (measured at the time of eligibility verification); • Primary hematological disorder (e.g. myelodysplastic syndrome, myeloma, sickle cell anemia, hematological malignancy, multiple myeloma hemolytic anemia); • known resistance to the rHuEPO defined by a requirement > 450 IU/kg/week by IV or 300 IU/kg/week by SC, equivalent to approximately 20.000 IU/week SC and in absence of iron deficiency; • who have suffered an event of active bleeding in the 30 days prior to the beginning of the study; • Morbid obesity, defined by a Body Mass Index (BMI) > 37 kg/m² in women and > 40 kg/m² in men.

Pre Intervention
	
Pre-intervention treatment with iron will be of interest to reach a transferrin saturation percentage (TSAT) $\geq 20\%$ and a ferritin ≥ 200 ng/ml.
 
According to the KDIGO guidelines [41], if the TSAT is <20% and the serum ferritin <200 ng/ml (<200 $\mu\text{g/l}$) and an increase in Hb concentration without starting ESA treatment is desired, it is suggested to administer a trial of IV iron.
 
IV iron may be provided as a single large dose or as repeated smaller doses depending on the specific IV iron preparation used (with the highest single dose varying by specific formulation). It is common practice to provide an initial course of IV iron amounting to approximately 1000 mg; this may be repeated if an initial dose fails to increase Hb level and allow a decrease in ESA dose and if the TSAT remains <20% and serum ferritin remains <200 ng/ml (<200 mg/l)

Randomization
	
Cluster Randomization Method will be used to randomize patients in the study. The randomization monitor will create unblinding envelopes and packaged the drug with blinded labels. After the randomization, each patient will be given an identification code in order to be recognized

	during the study and the treatment will be started based on allocated group of intervention.
Blinding	To prevent the influence of knowing intervention group on study conclusion, the Subjects and those who assess the study outcomes will be unaware of the state of the patient with regard to receiving the active drugs or standard remedy. For this purpose, Subjects and administrator of drug will be blinded by using a similar masked prefilled syringes. All drugs packages will be identified by unique numbers.
Intervention	The treatment proposed in this study was elaborated according to the KDIGO guidelines. Before the beginning of the protocol, for the patient to be able to enter the treatment, it shall be controlled that the iron (Fe) stores are adequate. In addition to main intervention, Nephrovit tablet /daily and B12 100 mcg (Amp)/monthly will be prescribed.
Outcomes	
Efficacy outcomes
 
Primary outcomes:
 
 • The mean Hb change level during the last 4 weeks of treatment • The mean weekly epoetin dosage per kg body weight during the last 4 weeks of treatment necessary to maintain the Hb level within 10-12 g/dl during the last 4 weeks of treatment will be considered as a second primary endpoint 
Secondary outcomes:
 
 • The proportion of patients with any permanent or transient dose change during main study phase, • The proportion of patients with any Hb measurement outside the target range, • Incidence of blood transfusions. • Proportion of patients with treatment success (Hb concentration ≥ 11.0 g/dl AND two consecutive weeks without any blood transfusion within the preceding 3 months), • Proportion of patients with maintenance success (maintenance of mean Hb concentration of 11.0 ± 1.0 g/dL for at least 4 consecutive weeks), • Percentage of Hb measurements > 10.0 g/dL,

	
 • Percentage of hematocrit measurements >30% 
Safety outcomes:
 
 • The incidence of Hb levels above 13 g/dL, • Proportion of patients with an increase in Hb concentration of > 1.0 g/dL for 4 consecutive weeks, • Incidence rate of adverse events
--	---

References:

1. Astor, B.C., et al., Association of kidney function with anemia: the Third National Health and Nutrition Examination Survey (1988-1994). Archives of internal medicine, 2002. 162(12): p. 1401-1408.
2. Brittin, G., et al., Stability of blood in commonly used anticoagulants. Use of refrigerated blood for quality control of the Coulter Counter Model S. American journal of clinical pathology, 1969. 52(6): p. 690-694.
3. Locatelli, F., et al., Revised European best practice guidelines for the management of anaemia in patients with chronic renal failure. Nephrology, dialysis, transplantation: official publication of the European Dialysis and Transplant Association-European Renal Association, 2004. 19: p. ii1-47.
4. Wintrobe, M.M. and J.P. Greer, Wintrobe's clinical hematology. Vol. 1. 2009: Lippincott Williams & Wilkins.
5. Weiss, G. and L.T. Goodnough, Anemia of chronic disease. New England Journal of Medicine, 2005. 352(10): p. 1011-1023.

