## 4. Section 4: Analysis

### 4.1. Outcome definitions

#### 4.1.1. Specification of outcomes and timings

Primary outcomes:

The primary efficacy endpoints will be analyzed using per-protocol (PP) analysis.

The mean Hb change level during the last four weeks of treatment is considered as the primary endpoint of the study.

The mean weekly epoetin dosage per kg body weight during the last four weeks of treatment necessary to maintain the Hb level within 10-12 g/dl during the last four weeks of treatment is considered as the second primary endpoint.

Secondary outcomes:

- The secondary variables will be analyzed using the ITT population.
- The proportion of patients with any permanent or transient dose change during main study phase is considered as the first secondary endpoint.
- The proportion of patients with any Hb measurement outside the target range is considered as the second secondary endpoint.
- The incidence of blood transfusions is considered as the third secondary endpoint.
- The proportion of patients with treatment success (Hb concentration  $\geq 11.0$  g/dl and two consecutive weeks without any blood transfusion within the preceding three months) is considered as the fourth secondary endpoint.
- The proportion of patients with maintenance success (maintenance of mean Hb concentration of  $11.0 \pm 1.0$  g/dl for at least four consecutive weeks) is considered as the fifth secondary endpoint.
- Percentage of Hb measurements  $> 10.0$  g/dl is considered as the sixth secondary endpoint.
- Percentage of hematocrit measurements  $> 30\%$  is considered as the seventh secondary endpoint.

Safety outcomes:

The incidence of Hb levels above 13 g/dl is considered as the first safety endpoint. Patients with at least one Hb measurement above 13 g/dL from week 2nd to week 26th will be taken into account to calculate this proportion.

---

The proportion of patients with an increase in Hb concentration of > 1.0 g/dl for four weeks is considered as the second safety endpoint.

Adverse events will be reported as incidence rate.

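### The treatment-success definition accepts any two transfusion-free weeks in the past three months and gives no assessment time, so a haemoglobin level reached by transfusion or already present at entry can count as success

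*Protocol*

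**What the plan says.** The Outcomes row of the Protocol synopsis lists, among the secondary outcomes: "Proportion of patients with treatment success (Hb concentration ≥ 11.0 g/dl AND two consecutive weeks" and so on, the transfusion part in full being "two consecutive weeks without any blood transfusion within the preceding 3 months". SAP 4.1.1 repeats it as the fourth secondary endpoint, "two consecutive weeks without any blood transfusion within the preceding three months", and adds nothing on timing. Neither document names a visit, a number of Hb readings, or where in the three months the two weeks must fall.

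Two entry criteria bear on this. The inclusion criteria admit "Hb level 8- 11.5 g/dl". The exclusion criteria bar "Any red blood cell transfusion during the last 3 months", judged when eligibility is verified.

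Other endpoints in the same lists are better specified. In SAP 4.1.1, Hb above 13 g/dl is counted from week 2 to week 26, and maintenance success carries a four-week duration. "Incidence of blood transfusions" is a separate secondary outcome.

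**The concern.** A transfusion clause in a success definition should stop a patient being credited to the drug when donor blood raised the Hb. This clause barely does that. The capitalised AND separates it from the Hb criterion, so the two weeks describe a transfusion-free spell, and any such spell in the look-back will do. It need not be the most recent one or include the day of the Hb reading.

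With no assessment time, two analysts could also obtain different success rates from the same data. And because the entry range reaches past 11.0 g/dl, some patients can satisfy the definition without any rise in Hb.

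Both routes add successes that do not reflect drug effect. SAP 3.2 and 4.1.1 analyse secondary variables in the ITT population, so that choice does not remove transfused patients. If the weaker product led to more transfusions, its patients could still be scored as successes, which would narrow the difference between arms.

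**Working it through.** The plan states no figure for treatment success, so there is none to reproduce. The sample size of 156 concerns the mean Hb comparison and does not enter here.

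**1. How many transfusions does it take to fail the clause?** Take three months as 91 days (13 weeks) and two weeks as 14 days.

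- With k transfusion days, 91 − k free days are split into k + 1 gaps (some possibly empty), so the longest gap is at least (91 − k)/(k + 1).
- k = 5: 86/6 = 14.3, so some gap is longer than 14 days and the clause is met whatever the timing.
- k = 6: 85/7 = 12.1, so failure becomes possible. One transfusion every 14 days leaves gaps of at most 13 days.
- Counting in whole weeks gives the same answer: of 13 weeks, at least 6 must contain a transfusion before no two adjacent free weeks remain.
- Reading three months as 89 to 92 days does not change the k = 5 result: 84/6 = 14.0 and 87/6 = 14.5.
- Six is only the minimum. With transfusion days placed at random in 91 days (40,000 simulated patients per count), 99.9% of patients with eight transfusions still met the clause.

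**2. What does the entry criterion contribute?** The Participants timeline puts screening at day −28 to 0. The earliest verification, day −28, is the least favourable case for this argument. The look-back starts at visit day − 91. Everything from there to verification is already free of red-cell transfusion by eligibility.

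| Visit | Day | Look-back starts | Free days up to day −28 |
|---|---|---|---|
| Week 2 | 14 ± 2 | −79 to −75 | 47 to 51 |
| Week 4 | 28 ± 2 | −65 to −61 | 33 to 37 |
| Week 6 | 42 ± 2 | −51 to −47 | 19 to 23 |
| Week 8 | 56 ± 2 | −37 to −33 | 5 to 9 |

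Through week 6 the clause is met however many transfusions are given on study. With verification at day 0, the week 8 figure becomes 33 to 37 days, so the clause is met there too. This assumes that the look-back may reach before randomisation, which neither document rules out.

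**3. How many patients meet both components at entry?** The overlap is 11.0 to 11.5 within 8 to 11.5 g/dl. The documents give no baseline distribution, so each share is an assumption.

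- Uniform: (11.5 − 11.0)/(11.5 − 8) = 0.5/3.5 = 14.3%, about 22 of 156.
- Normal with mean μ and SD σ, truncated to 8–11.5: share = [Φ((11.5 − μ)/σ) − Φ((11.0 − μ)/σ)] / [Φ((11.5 − μ)/σ) − Φ((8 − μ)/σ)].
- Example, μ = 10, σ = 1.0: (0.933 − 0.841)/(0.933 − 0.023) = 10.1%.
- μ from 9.5 to 10.5 and σ from 0.8 to 1.2: about 2.5% to 18%, or 4 to 28 of 156.
- μ from 9 to 11, same σ: 0.6% to 32%.

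**4. What could the overlap do to the comparison?** Suppose a share q in each arm qualifies at entry and all of them are scored as successes. The observed difference is then (1 − q) times the difference among the rest. For q of 2.5% to 18% the factor is 0.975 to 0.82. This is an upper limit on the dilution from this source, since such a patient can still fall below 11.0 g/dl and fail a later assessment.

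**The case against.** The strongest objection concerns intent. The words after the AND could be a misplaced phrase: Hb of at least 11.0 g/dl for two consecutive weeks, with the whole preceding three months free of transfusion. That would mirror the exclusion criterion, and on that reading the plan needs only clarification. The intent is plausible, but neither document says it, and getting there takes the same rewording.

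A reader might infer three stronger things that the documents do not support.

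- *Two transfusion-free weeks are enough for success.* They are not. Hb of at least 11.0 g/dl is still required, so a repeatedly transfused patient counts only if Hb gets there.
- *Patients are scored as successes before their first dose.* Neither document says that a Day 1 reading counts. Some patients meet the criteria at entry; whether that reading would be used is undefined.
- *The endpoint could conceal an inferior product.* SAP 4.2.1 rests the non-inferiority decision on mean Hb change. Treatment success is one of seven secondary endpoints, tested by chi-square or Fisher's exact test with no margin, and excess transfusion would show in its own endpoint.

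The practical effect may also be small if transfusions are rare. The documents give no rate. At an assumed 1% per week, 0.99^13 = 88% of patients would have no transfusion in 13 weeks; at 0.5%, 0.995^13 = 94%. The literal and the strict reading of the transfusion clause would then differ for at most about 12% or 6% of patients, and fewer once the Hb condition applies. This limits the size of the problem. It does not make the clause do its job.

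**Conclusion.** The definition is wrong as written, and the fault is confined to a secondary endpoint. That the transfusion component excludes almost no one follows from the wording and arithmetic alone: five or fewer transfusions in three months always pass, and through week 6 the entry criterion guarantees a pass provided the look-back may reach before randomisation. An Hb of 11.0 g/dl or more reached through transfusion can therefore be counted.

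The missing assessment time and the overlap with the entry range are plain in both documents. The size of the overlap is not: 14% under a uniform distribution and about 2.5% to 18% under the truncated normals above are assumptions.

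The reported success proportions may be inflated and a difference between arms diluted. By how much cannot be fixed from the documents, since they give neither a transfusion rate nor a baseline Hb distribution. The primary analysis and the sample size stand.

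**What to change.** In the Outcomes row of the Protocol synopsis and in SAP 4.1.1, replace the definition with: *Hb ≥ 11.0 g/dl at two consecutive scheduled measurements in the last four weeks of treatment, with no blood transfusion in the 3 months before the first of them.* The sponsor should confirm that this is the intended meaning. The threshold and the three-month window stay as they are.

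The schedule allows it. The timeline marks treatment through week 24, with visits at weeks 20, 22 and 24. A look-back from day 140 starts at day 140 − 91 = 49, wholly on treatment. The timeline has no separate row for Hb, so the sponsor should confirm that it is measured at these visits.

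The rewording still counts a patient who enters at 11.0 to 11.5 g/dl and stays there. The success proportion should therefore also be reported separately for patients with baseline Hb below 11.0 g/dl.

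The cost is one definition changed in two documents and one extra line of results. Hb and transfusions are already needed for other endpoints. The reported success rate will be somewhat lower.

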Drug accountability		×	×	×	×	×	×	×	×	×	×

## **1. Section 1: Administrative information**

### **1.1. Title and Trial registration**

#### **1.1.1. Descriptive title that matches the protocol, with ‘Statistical analysis plan’ either as a fore runner or sub title, and trial acronym**

Statistical analysis plan for the Phase III, randomized, two armed, multicenter, parallel, double blind (patient and assessor blinded), active controlled non inferiority clinical trial to determine the non-inferior therapeutic efficacy and safety between CinnaPoietin® (Beta erythropoietin) and Eprex® (epoetin alpha) on treatment of anemia in ESRD hemodialysis patients.

